6.2.1.1 Confirmatory analysis of the primary efficacy variable

The primary efficacy variable will be analyzed descriptively in frequency tables by treatment period and region within each treatment group. Additionally, vilaprisan treatment after 12 weeks, i.e. in TP1, of treatment groups A1 and B2 will be pooled.

The confirmatory analysis will be performed only based on TP1. In the confirmatory analysis, the proportion of subjects with amenorrhea will serve as comparison criteria in the comparisons defined in Section 6.2. For simplicity, the confirmatory analysis will be formulated generally. The null hypothesis, H_0 , states that the common difference of proportions between the 2 mg vilaprisan group and the placebo group among the regions (US, Japan and other) δ is zero. Considering a two-sided test problem with hypotheses

$$H_0: \delta = 0$$
 vs. $H_1: \delta \neq 0$,

the alternative hypothesis, H_1 , states that the common difference of the proportion of subjects with amenorrhea between the 2 mg vilaprisan group and the placebo group among the regions is unequal to zero.

The test problem will be investigated by means of a two-sided, continuity-corrected Cochran-Mantel-Haenszel (CMH) test stratified by country/region at a local 0.05 significance level. The test statistic of the CMH test is defined as

$$CMH = \frac{\left[\left|\sum_{k} \left(n_{11k} - E_{H_0}(n_{11k})\right)\right| - 0.5\right]^2}{\sum_{k} \operatorname{Var}_{H_0}(n_{11k})},$$

with n_{ijk} representing the number of subjects with (i = 1) or without amenorrhea (i = 0) and belonging to the vilaprisan group (j = 1) or to the placebo group (j = 0) and country/region k $(1 \cong US, 2 \cong Japan, 3 \cong$ other countries). It compares the observed number of subjects with amenorrhea in the vilaprisan 2 mg group with the expected number under the null hypothesis [3]. Under the assumption of fixed $n_{1+k} = \sum_{j=0}^{1} n_{1jk}$, the expected number and the variance under the null hypothesis are [4]

$$\mathcal{E}_{H_0}(n_{11k}) = n_{1+k} n_{+1k} / n_{++k}$$

and

$$\operatorname{Var}_{H_0}(n_{11k}) = \frac{n_{1+k}n_{0+k}n_{+1k}n_{+0k}}{n_{++k}^2(n_{++k}-1)}$$

The plus sign (+) denotes a summation over the respective index.

Under the said assumption and the null hypothesis, the CMH test-statistic approximatively follows the χ^2 -distribution with one degree of freedom [3]. Hence, the null hypothesis of conditional independence between the treatment and the presence of amenorrhea given the country/region will be rejected, if the observed test-statistic exceeds the 95% quantile of the χ^2 -distribution with one degree of freedom, which is 3.841.

Along with the results of the CMH test, the Mantel-Haenszel estimate for the common risk difference of the proportion of subjects with amenorrhea between the 2 mg vilaprisan group and the placebo group among the regions δ will be reported together with its approximate 95% confidence interval (two-sided).

The Mantel-Haenszel estimator for the common risk difference

$$\hat{\delta} = \frac{\sum_k \hat{\delta}_k w_k}{\sum_k w_k},$$

is composed of the estimated risk difference of the proportion of subjects with amenorrhea in country/region k,

$$\hat{\delta}_k = \frac{n_{11k}}{n_{+1k}} - \frac{n_{10k}}{n_{+0k}},$$

and country/region-specific weights

$$w_k = \frac{n_{+1k} \, n_{+0k}}{n_{++k}} \, [5].$$

$$\left[\hat{\delta} \pm \mathbf{z}_{\alpha/2} \sqrt{\widehat{Var}(\hat{\delta})}\right],$$

where $z_{\alpha/2}$ denotes the ($\alpha/2$)-quantile of the standard normal distribution and the variance estimator of the Mantel-Haenszel estimator $\hat{\delta}$ will be computed as

$$\widehat{Var}(\widehat{\delta}) = \frac{\widehat{\delta}\sum_{k} u_{k} + \sum_{k} v_{k}}{(\sum_{k} w_{k})^{2}},$$

where

$$u_k = \left[n_{+1k}^2 n_{10k} - n_{+0k}^2 n_{11k} + \frac{n_{+1k} n_{+0k} (n_{+0k} - n_{+1k})}{2} \right] / n_{++k}^2$$

and

$$v_k = \frac{n_{11k}(n_{+0k} - n_{10k}) + n_{10k}(n_{+1k} - n_{11k})}{2n_{++k}} [6]$$

6.2.1.2 Sensitivity analyses of the primary efficacy variable

6.2.1.2.1 Analysis in PPS population

As a first sensitivity analysis, the impact of the choice of analysis set will be investigated. The confirmatory analysis of the primary efficacy variable will thus be repeated on the PPS population excluding subjects with validity findings impacting the assessment (see Section 5.1) of amenorrhea during the last 28 days of TP1. As opposed to the analysis on the FAS, this is intended to measure the actual effect in protocol adherers rather than investigating the effect of the treatment strategy in every randomized subject.

6.2.1.2.2 Analysis based on alternative missing data imputation strategy

The impact of missing data will be investigated in the FAS (according to the intention to treat principle) with multiple imputation, using a pattern-mixture framework as described by the National Research Council (NRC 2012) [7]. In the primary analysis, it is assumed that values in the UF-DBD or for the AH method are missing at random (MAR), i.e., they only depend on observed outcomes and can thus be imputed based on the observed data. However, it is possible that missing values are systematically different from observed values because patients are dissatisfied with their treatment and are consequently more likely to withdraw from the study, for example. If the differences between missing and observed values do not balance out between the treatment groups, then this creates a bias in the treatment effect. Therefore, this sensitivity analysis serves to examine the missing data mechanism and explore different scenarios under a MNAR (Missing Not at Random) assumption where an outcome depends on the fact whether it is observed or not and missing outcomes can thus differ systematically from observed outcomes by treatment group.

For the purpose of this sensitivity analysis for missing data, the standard procedure of imputing intermittent single or two consecutive days with missing UF-DBD bleeding intensities and the replacement of missing daily AH values with 0 mL for bleeding intensities of not more than 'spotting' are kept as sensible approaches because nothing out of line is expected to happen in the time frame of one or two days. In contrast to the primary analysis, however, days with biopsies and the three days thereafter will not be considered with an AH value of 0 mL (assuming no bleeding), but will be considered missing since the AH values on those days if the patient had not had the biopsy are unknown. This rule and further rules used to impute missing data in the primary analysis will be challenged with this analysis using multiple imputation in a pattern-mixture approach.

Subjects are sorted into three categories based on the available UF-DBD and AH information from Day 57 to 84 of the TP1 (or the last 28 days of TP1, if study drug was taken for more than 84 days). Those three categories are comprised of clear responders and clear non-responders (after the initial minimal imputation rules described above) as well as subjects with unclear response status. A clear responder for amenorrhea is defined as a subject

- who has only UF-DBD bleeding intensities of no more than 'spotting' AND
- for whom the sum of daily AH values is less than 2 mL AND
- for whom there are no missing values for either the AH method (daily values) or the UF-DBD bleeding intensities.

As opposed to this definition, a clear non-responder for amenorrhea is defined as a subject

- who has at least one bleeding intensity of 'mild' or higher OR
- for whom the sum of daily AH values is equal to or higher than 2 mL.

All response criteria are set in relation to the planned time frame for the assessment of the primary efficacy variable, i.e., Day 57 to Day 84 of the TP1. An exception is made when a subject's TP1 is longer than 84 days. In this case the last 28 days of TP1 are used for the assessment.

A subject is considered as unclear responder for amenorrhea (and thus having a missing outcome) if in the relevant time frame, all the subject's bleeding intensities do not exceed 'spotting' and the sum of daily bleeding intensities is below 2 mL, but there are still missing values among both the UF-DBD bleeding intensities and the daily AH values between Day 57 and 84 of the TP1. Therefore, it is still possible that replacement of the missing bleeding information turns an apparent responder into a non-responder for amenorrhea, signifying that no clear assessment about the response status can be made.

A descriptive analysis of the number of subjects in each response category will be supplied by treatment group.

Missing data imputation will only be applied to subjects with unclear response status, whereas not the AH values will be imputed but the response status. Response status of subjects with unclear outcome are generated in a three-step process [8] by

- 1) Estimation of individual log-odds of amenorrhea for all patients from a logistic regression model, which is an imputation model fitted based on data of clear responders and non-responders,
- 2) Simulation of response status using the predicted log-odds to create multiple datasets with imputed data; conduct of the Cochran-Mantel-Haenszel test on each imputed dataset; combination of the analysis results to generate statistical inference,

3) Assessment of the robustness of step 2 after adding/subtracting a penalty (shift parameter) from the log-odds in the placebo group and vilaprisan group, respectively, and determination of the "tipping point".

Those three steps are outlined in more detail in the following.

Step 1:

To impute the missing response status, a logistic regression model will be fitted to the binary variable amenorrhea yes/no (coded as 1 and 0) for subjects who are either clear responders or clear non-responders. Treatment group (X_T) , stratification factor region (X_R) , baseline covariates age (X_{Age}) and baseline MBL (X_{BMBL}) are used as covariates. This leads to the following model equations for the log-odds $logit(p_1) = log(p_1/(1 - p_1))$ of the response (amenorrhea=yes) probability p_1 :

$$logit(p_1) = \beta_0 + \beta_1 X_T + \beta_2 X_R + \beta_3 X_{Age} + \beta_4 X_{BMBL}$$

If the model does not converge, the stratification factor region will not be used as covariate in the model.

Step 2:

Following the multiple imputation approach with the monotone logistic regression method [9], new parameters $\beta_* = (\beta_{*0}, ..., \beta_{*4})'$ are drawn from the posterior predictive distribution of the regression parameters $\beta = (\beta_0, ..., \beta_4)'$. For a subject with unclear response status and covariate vector $x = (1, x_T, x_R, x_{Age}, x_{BMBL})'$ the predicted response probability of amenorrhea is given by

$$p_1 = \frac{\exp(x'\beta_* + \delta)}{1 + \exp(x'\beta_* + \delta)},$$

where δ denotes the penalty or shift parameter which is 0 under the MAR assumption. A random variable u is drawn from a standard uniform distribution and if the unequality $u < p_1$ holds for a subject then the subject's response status for amenorrhea is imputed with yes (=1), else it is imputed with no (=0). After imputing all subjects' response statuses in this manner, the primary analysis is repeated, i.e., the Cochran-Mantel-Haenszel test is conducted based on the complete imputed data set. This imputation and analysis will be repeated 1,000 times. Inferences for combined parameters will be done using Rubin's multiple imputation rules [10] which reflect imputation uncertainty.

Step 3:

To assess the robustness of the analyses for deviations from the MAR assumption, step 2 will be repeated with different choices of the shift parameter for subjects from the vilaprisan group and placebo group, respectively. To explore the whole range of possibilities unfavorable to vilaprisan, choices of non-positive shift parameters $\delta_v = 0, -1, -2, ..., \pi_{min}, \pi_{min} < 0$, for the log-odds of subjects with unclear response status in the vilaprisan group will be combined with choices of non-negative shift parameters $\delta_p = 0, 1, 2, ..., \pi_{max}, \pi_{max} > 0$, for the logodds of subjects with unclear response status in the placebo group. The combination $\delta_v = 0$ and $\delta_p = 0$ signifies a MAR assumption and represent the "best case" among the presented scenarios. In this scenario, patients with unclear response status are assumed to have the same chance of amenorrhea as similar patients for whom response status is known. Any combinations different from $\delta_v = 0$ and $\delta_p = 0$ refer to the situation where unobserved bleeding is missing not at random (MNAR), with larger absolute values for the penalities

indicating larger deviations from the MAR assumption. Values of $\delta_v < 0$ are equivalent to a multiplication of the odds (chance) of having amenorrhea with the factor $\exp(\delta_v)$ and imply vilaprisan patients with unclear response status have a systematically lower chance of amenorrhea than similar patients with clear response status. Choices of $\delta_p > 0$ or, equivalently, multiplication of the odds with $\exp(\delta_p)$ imply that placebo patients with unclear response status have a systematically higher chance of amenorrhea than those with clear response status. Therefore, a combination of $\delta_v = \pi_{min} < 0$ and $\delta_p = \pi_{max} > 0$ represents the "worst case" among these scenarios in which all subjects with unclear response status in the vilaprisan group are set to responders whereas all subjects with unclear response status in the placebo group are set to responders for amenorrhea.

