##### 10.3.1.1 Primary efficacy variable

*This section was changed in Amendment 1, see Section 15.1.1*

The primary efficacy variable is amenorrhea (yes/no), defined as MBL < 2 mL during the last 28 days of treatment.

If an endometrial biopsy was conducted during this time period, bleeding on the day of biopsy and the 3 days thereafter will not be considered in this evaluation.

For the primary analysis, the amenorrhea rates at the end of Treatment Period 1 of all Treatment Groups will be used.

Subjects who discontinue treatment prior to completion of treatment Week 8 of the respective treatment period will be considered not having amenorrhea.

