4.3.1 Bleeding data

The following rules for the handling of missing vaginal bleeding data pertains to bleeding data assessed by the AH method, the menstrual pictogram (MP, see Appendix 1) or the item "Rate the severity of **any vaginal bleeding** in the past 24 hours" (on a 6-point Likert scale) in the Uterine Fibroid Daily Bleeding Diary (UF-DBD, see Appendix 2). The resulting data forms the basis for the primary, the secondary and bleeding-related other efficacy variables (see Section 6.2).

On days without bleeding, no collection of sanitary products for the AH value determination was asked for. The UF-DBD is used for the identification of these non-bleeding days. Thus, missing AH/MP values on days where the UF-DBD recorded the bleeding intensity as "No vaginal bleeding" or "Spotting" will be set to 0 mL.

Missing bleeding data in the subjects' diaries will be imputed. First, missing bleeding intensities in the UF-DBD will be imputed. Missing bleeding intensities will only be imputed if values are missing for a single or for two consecutive days. For the UF-DBD, a type of 'worst case approach' will be used for imputing missing bleeding intensities. The approach consists in replacing the missing value(s) by the maximum of the bleeding intensities of the day before and the day after the day(s) with missing value(s).

After having imputed missing values in the UF-DBD, missing AH/MP values are imputed in the next step.

For days with bleeding intensity of 'mild' or higher in the UF-DBD, missing AH/MP values will be replaced by the mean value of AH/MP values of the days with the same bleeding intensity. In case there are no AH/MP values with the same bleeding intensity, the mean of the AH/MP values of next higher intensity will be used. In case there is no intensity higher than the bleeding intensity of the missing AH/MP values available, no replacement for the missing AH/MP values will be done for such days, but if at least one such day occurs within the respective 28 days of treatment for a subject, the subject will be considered as not having amenorrhea.

In case blood loss could not be measured by the vendor for a sanitary product, the missing value will be replaced by the mean blood loss measured for the same type of sanitary product for this specific subject.

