Abbreviations: HMB: Heavy menstrual bleeding, CMH: Cochran-Mantel-Haenszel, H: Hypothesis to be tested related to the amenorrhea (H₁), HMB response (H₂), time to onset of amenorrhea (H₃) or time to onset of controlled bleeding (H₄), TP: Treatment period, A1: Vilaprisan 2mg; 2 treatment periods of 12 weeks, B1: Placebo; 1 treatment period of 12 weeks and Vilaprisan 2mg; 1 treatment period, B2: Vilaprisan 2mg; 1 treatment period of 12 weeks and placebo; 1 treatment period.

The study will be considered successful if at least superiority of vilaprisan 2 mg vs. placebo in Treatment Period 1 (TP1) based on the primary efficacy variable can be demonstrated. In general, superiority of vilaprisan treatment is shown if the respective null hypothesis is rejected to a local alpha level of 0.05 and point estimates of treatment effect favor vilaprisan.

The primary analysis will be conducted based on the FAS (see Section 5.1).

6.2.1 **Primary efficacy variable**

The primary efficacy variable is amenorrhea (yes/no), defined as MBL <2 mL during the last 28 days of treatment. Evaluation of MBL will be based on AH method for a treatment period of interest.

The primary efficacy variable will be derived after the imputation of missing values described in Section 4.3.

If after the imputations described in Section 4.3 and considering potential biopsies, neither of the AH values for the last 28 days are missing, AH values and bleeding intensities of the last 28 days of a treatment period are used to derive the primary efficacy variable.

If, in contrast, there are AH values in the last 28 days of treatment which are still missing (i.e., where an imputation was not possible), it is further studied whether the corresponding bleeding intensities of the UF-DBD are missing on the same day(s) as well.

- (a) If the bleeding intensity is not missing and only the AH value is missing, the bleeding intensity must be at least 'mild', because for 'no vaginal bleeding' and 'spotting' the AH value would have been imputed with 0 mL. Accordingly, it must be assumed that bleeding has occurred on these day(s). Therefore, the subject is considered as not having amenorrhea. Step b) will then not be applied irrespective of whether there are also days for which both, the bleeding intensity and the AH value, are missing.

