- (b) If both, the bleeding intensity and the AH value, are missing for any of the last 28 days, the 28-day period will be extended: The left margin of the 28-day period will be displaced backwards in time and step-wise until the required number of 28 non-missing AH values are included. The left margin may be displaced backwards at maximum up to the end of the first bleeding episode when treatment was started in respective treatment period.

Considering this time window, a subject will be considered as not having amenorrhea if

- i) the sum of the non-missing (i.e. original or imputed) AH values is ≥ 2 mL, or
- ii) there is at least one day with missing AH value and bleeding intensity of 'mild' up to 'very severe' after having applied the imputation rules, or
- iii) the subject did not complete at least 8 weeks of treatment.

If neither of i), ii) or iii) applies, the subject will be considered as having amenorrhea.

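### The missing-data sensitivity analysis uses a stricter endpoint than the primary: a measured 'mild' diary day fails a woman whose AH total is below 2 mL, so its zero-shift run need not match the primary result even with complete data

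*SAP*

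**What the plan says.** **Primary endpoint.** Protocol 10.3.1.1 defines it by volume alone: "The primary efficacy variable is amenorrhea (yes/no), defined as MBL < 2 mL during the last 28 days of treatment". Under SAP 6.2.1 a woman fails in three ways only: her AH values sum to 2 mL or more; "there is at least one day with missing AH value and bleeding intensity of 'mild' up to 'very severe" remains after imputation; or she did not complete 8 weeks of treatment. Otherwise she has amenorrhea. Protocol 10.3.3 gives the same rule. Even a 'mild' day without an AH value need not fail her, because under SAP 4.3.1 "missing AH/MP values will be replaced by the mean value of AH/MP values of the days with the same bleeding intensity".

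**Sensitivity analysis.** SAP 6.2.1.2.2 looks at Days 57 to 84 of Treatment Period 1, or the last 28 days if treatment ran longer. It uses three categories:

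- Clear responder: a subject "who has only UF-DBD bleeding intensities of no more than 'spotting' AND" with an AH sum below 2 mL and nothing missing.
- Clear non-responder: a subject "who has at least one bleeding intensity of 'mild' or higher OR" with an AH sum of 2 mL or more.
- Unclear: no day above 'spotting' and a sum below 2 mL, but "there are still missing values among both the UF-DBD bleeding intensities and the daily AH values".

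Only unclear women are imputed. Clear responders and clear non-responders supply the data for the imputation model and enter every repeat of the CMH test unchanged. The section describes itself as a study of missing data that challenges the rules used to impute it. The one change in handling that it contrasts with the primary analysis is that biopsy days, with the three days after, become missing instead of 0 mL.

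**The concern.** A 'mild' day with a measured AH value is not missing data. Failing a woman on it changes the outcome variable: it adds a diary criterion that the SAP already analyzes separately, as the secondary variable absence of bleeding (spotting allowed).

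The run with both shifts at zero is labelled as the missing-at-random case, and a reader will compare it with the primary result to judge how much missing data matter. With the categories as written, that comparison mixes a stricter endpoint with a missing-data assumption. The planned table counts women in the three categories; it does not show how many clear non-responders failed on 'mild' alone. The altered outcome also feeds the imputation model, so it moves the predicted probabilities of the unclear women before any shift is applied. This is the SAP's only model-based check of missing data for the primary endpoint.

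**Working it through.** **1. Both rules applied to the same complete record** (27 days without bleeding at 0 mL, plus one 'mild' day with measured AH):

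| AH on the 'mild' day | Primary (SAP 6.2.1) | Sensitivity (SAP 6.2.1.2.2) |
|---|---|---|
| 0.3, 0.8, 1.5 or 1.99 mL | amenorrhea | clear non-responder |
| 2.0 mL | no amenorrhea | clear non-responder |

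Two 'mild' days of 0.8 mL (sum 1.6 mL) also give opposite answers. No assumption is needed for this step.

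Small volumes are possible. In SAP Appendix 1 the lightest pictogram is below 2 mL for 11 of 12 products (0.16 to 1.36 mL). The table does not show how women would rate such a stain in the diary.

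**2. Size with nothing missing.** Let f be the share of AH responders with a measured 'mild' day. The documents do not give f, so every value here is an assumption. The difference becomes

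pv × (1 − fv) − pp × (1 − fp).

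Protocol 10.4 plans for a difference of at least 0.4; the split 0.60 versus 0.20 is assumed. The ASTEROID 1 regional rates in Protocol 10.4 are 0.7/0.9/0.9 versus 0.2/0.0/0.1. The planned sizes are 104 versus 52 (strata 52/26/26 and 26/13/13). The test is the SAP's continuity-corrected CMH on expected counts, critical value 3.841.

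| f, same in both arms | Difference, 0.60 vs 0.20 | Chi-square | Difference, ASTEROID 1 rates | Chi-square |
|---|---|---|---|---|
| 0 | 0.40 | 20.3 | 0.675 | 61.2 |
| 5% | 0.57 − 0.19 = 0.38 | 18.4 | 0.641 | 54.3 |
| 10% | 0.54 − 0.18 = 0.36 | 16.7 | 0.608 | 48.2 |
| 20% | 0.48 − 0.16 = 0.32 | 13.6 (p = 0.0002) | 0.540 | 38.0 |

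If f differs by arm, the direction can change. From 0.40, f = 10% in vilaprisan only gives 0.54 − 0.20 = 0.34 (chi-square 14.7); in placebo only it gives 0.60 − 0.18 = 0.42 (22.5).

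Protocol 10.4 says the planned size was not reached. At an assumed 52 versus 26 with 0.60 versus 0.20, p = 0.002 (f = 0), 0.006 (10%) and 0.014 (20%).

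**3. Effect on the imputation model at f = 10%.** The vilaprisan log-odds move by logit(0.54) − logit(0.60) = −0.245, or by logit(0.72) − logit(0.80) = −0.442. The shift grid moves in steps of 1, so the rule alone uses about a quarter to nearly half of a step.

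**4. Biopsy days.** SAP 6.2.1.2.2 makes these days missing but also keeps the replacement of missing AH by 0 mL when the diary shows 'spotting' or less. For a woman with a complete diary of 'spotting' or less and no other gaps:

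- Diary and AH both blanked: she is unclear.
- AH alone blanked, 0 mL replacement retained: she is a clear responder, and the announced biopsy change has no effect for her.
- AH alone blanked, 0 mL replacement suspended: she is not clear, and not unclear either, because nothing is missing in the diary. She has no category.

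If the diary is not blanked and shows 'mild' on such a day, she is a clear non-responder, whereas SAP 6.2 resets that entry to no vaginal bleeding for the primary analysis.

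**The case against.** The rule is openly pre-specified in a secondary analysis, the primary result does not depend on it, and significance holds in every scenario shown. All of that stands.

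The statement in Step 2 that the primary analysis is repeated can fairly be read as naming the CMH test, not the endpoint derivation. Some information will also be available elsewhere: absence of bleeding and maximum intensity per 28 days are tabulated, and derived variables are listed by subject. A determined reader could reconstruct who failed on 'mild' alone, although no count is planned. The magnitude rests wholly on an assumed f, and a lightest stain might equally be rated 'spotting'.

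Four stronger readings are tempting, and the documents do not support them.

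- *The 'mild' rule is the only reason the zero-shift run can differ.* It is not. The biopsy-day change, the fixed Day 57 to 84 window without backward extension, and the absence of the 8-week failure rule also separate the two. For a woman with 84 treatment days, no biopsy and complete data those drop out and the 'mild' rule alone can reclassify her.
- *Women certainly fall outside the categories.* That follows from one of the three biopsy-day readings only. Elsewhere, missing AH normally goes with a missing diary entry, so requiring both is largely coherent. The documents do not say how many women had a biopsy in the window.
- *The rule is simply conservative against vilaprisan.* Its direction depends on f in each arm.
- *The tipping-point grid is wrong.* The Step 3 sentence that sets unclear vilaprisan women to responders in the worst case contradicts the section's own negative shifts. It is a slip; the grid is correctly specified.

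**Conclusion.** The concern holds on the text. SAP 6.2.1.2.2 fails a measured 'mild' day that SAP 6.2.1 and Protocol 10.3.1.1 and 10.3.3 would pass, and it does not say so. A difference between the zero-shift run and the primary result therefore could not be assigned to missing data.

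The size is unknown. Under assumed shares of 5% to 20% in both arms, the difference falls by 0.02 to 0.08 from 0.40, or by about 0.03 to 0.14 from 0.675, and the test stays significant. A reader might infer that the primary conclusion is in doubt; nothing here supports that. The damage is to the interpretation of the sensitivity analysis, which justifies correction before unblinding. The biopsy-day gap is an ambiguity to settle, and the wording slips are clerical.

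**What to change.** Rewrite the categories in SAP 6.2.1.2.2 so that a day with a measured AH value carries no diary condition:

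- *Clear non-responder:* non-missing AH values sum to 2 mL or more, or a 'mild' or heavier day has a missing AH value that cannot be replaced under SAP 4.3.1, as in rule (a) and criterion ii) of SAP 6.2.1.
- *Clear responder:* no missing AH or diary values, and an AH sum below 2 mL.
- *Unclear:* all others, including a 'mild' or heavier day whose AH value is missing but replaceable.

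Then state three things:

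1. Whether women with less than 8 weeks of treatment remain failures, as in criterion iii) of SAP 6.2.1, or are imputed. If imputed, label this a deliberate departure from the primary rule; otherwise definite primary failures could be drawn as responders unannounced.
2. Whether the biopsy-day rule blanks the diary as well as AH, and whether the 0 mL replacement still applies on those days.
3. If a diary-plus-AH definition is wanted, that it is a separate, labelled analysis.

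Wording: in the definition of unclear, "the sum of daily bleeding intensities is below 2 mL" should refer to daily AH values; in the Step 3 worst case, unclear vilaprisan women should be set to non-responders.

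Cost: text changes before unblinding, no new data, no change to the primary analysis, and one extra table if the stricter definition is kept. The downside is that more women may be unclear, so more rests on the imputation model.
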